This SAP has been developed and approved prior to database lock and data analysis. All analyses will be conducted after clinical trial data are entered into the database, discrepancies resolved, and the database is authorized (closed to further changes). Any deviations from the SAP will be documented as such in the study report.

Production and quality control of statistical analyses and accompanying tables, listings, and figures (TLFs) will be the responsibility of IQVIA Biotech located in Morrisville, North Carolina, United States.

II. Protocol Objectives

A. Primary

The protocol lists the following primary objective:

- To determine the safety and tolerability of brequinar and the DHODH inhibitory activity of brequinar in adult subjects with AML.

B. Secondary

The protocol lists the following secondary objectives:

- To determine the overall response rate (ORR) including complete remission (CR), CR with incomplete hematologic recovery (CRi), morphologic leukemia-free state (MLFS), partial remission (PR) (criteria as defined in the ELN Guidelines, by [Dohner et al., 2017](#)) and complete remission with partial hematological recovery (CRh).

- To assess the rate of overall survival (OS) and event-free survival (EFS).
- To evaluate duration of response (DOR).
- To characterize the pharmacokinetic (PK) profile of brequinar.
- To characterize the DHO plasma levels after oral dosing with brequinar.

C. Exploratory

The protocol lists the following exploratory objectives:

- To assess the relationship between DHODH inhibition and the efficacy and safety of brequinar.
- To evaluate molecular and cellular biomarkers that may be predictors of antitumor level and/or treatment resistance including cytogenetics, molecular profiling, and flow cytometry during and after treatment.
- To evaluate global gene expression profiles, deoxyribonucleic acid (DNA)methylation profiles, and other potential prognostic markers to explore predictors of antitumor activity and/or resistance to treatment.

III. Study Endpoints

A. Primary Endpoints

The study protocol defines primary endpoints as safety/tolerability and DHO level relationship with safety and therapeutic brequinar levels.

Safety/tolerability, assessed at each study visit using the Common Terminology Criteria for Adverse Events (CTCAE) version 4.03, will be evaluated for each subject as follows:

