- Through Day 42, Grade 3 or higher, treatment-emergent, study drug-related, non-hematologic AE will be considered unacceptable toxicity with the following exceptions:

Condition	Exception Description
Nausea/ Emesis	Grade 3 nausea and/or emesis resolving to less than or equal to Grade 2 or baseline within 1 week after the use of an optimal antiemetic regimen based on standard practice.
Diarrhea	Grade 3 diarrhea resolving to less than or equal to Grade 1 or baseline within 1 week after receiving the maximal supportive therapy based on standard practice.
Laboratory abnormalities	Asymptomatic Grade 3 laboratory abnormalities that are not considered to be clinically significant.
Mucositis	Grade 3 with duration < 1 week.
Fatigue	Grade 3 with duration < 2 weeks.

- After 42 days of treatment, criteria for unacceptable safety will be expanded to include hematologic AEs defined as:
 - Prolonged neutropenia with ANC < 500 from start of therapy in the absence of disease.
 - ≥ Grade 4 neutropenia.
 - And/or ≥ Grade 4 thrombocytopenia with a hypocellular bone marrow and no greater than 5% marrow blasts lasting for ≥2 weeks.
- After 42 days of treatment, in expansion cohort subjects, the definition of unacceptable safety will include signs of hepatotoxicity (an episode of > Grade 2 toxicity for ALT and AST).

B. Secondary Endpoints

The following secondary endpoints will be analyzed:

- ORR including CR, CRi, CRh, MLFS, or PR.
- Rates of OS and EFS.
- Duration of response.
- PK profile of brequinar.
- DHO plasma profile.

C. Exploratory Endpoints

The following endpoints will be explored:

- Relationship between DHODH inhibition and the efficacy and safety of brequinar.
- Antitumor level based on molecular and cellular biomarkers including cytogenetics, molecular profiling, and flow cytometry during and after treatment.
- Global gene expression profiles, DNA methylation profiles, and other potential prognostic markers to explore predictors of antitumor activity and/or resistance to treatment.

IV. Study Design

A. Design Overview

This will be a phase 1b/2a multi-center, open-label, non-randomized clinical trial to assess the safety, tolerability and efficacy of dose-adjusted brequinar in adult subjects with AML. The study will also assess the inhibition of DHODH and the PK profile of brequinar in plasma. Intra-subject dosing will be adjusted based on safety/tolerability, brequinar PK, and DHO levels.

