Up to 27 subjects are planned to be entered in this trial. Cohort 1 was planned to have 6 subjects, but enrollment was stopped after 5 subjects when brequinar PK and DHO results became available. These results led to study design changes as described here. The sixth subject will not be enrolled in Cohort 1.

Cohort 2 will enroll approximately 6 subjects, followed by an expansion cohort of approximately 15 subjects. All subjects in Cohort 2 will start with a 500 mg/m² dose once-weekly. Brequinar PK and DHO samples will be obtained for these subjects in Week 1 and results used to make decisions about the Week 2 once-weekly dose. Brequinar PK and DHO samples will also be obtained for Week 2 and the results used to make decisions about Week 3 dose frequency (once or twice-weekly) and the dose. The dose will be adjusted for each subject to meet the twice-weekly brequinar PK and 72-hour DHO criteria, and the Week 2 procedures may be repeated if needed until the twice-weekly dose is found.

After both the brequinar PK and 72-hour DHO level meet criteria described in the Individual Dose Adjustment Guidelines as described in Protocol Section 8.5, a subject may move to twice-weekly dosing on a continuing basis as tolerated. The twice-weekly dose may be further adjusted using 84-hour DHO (trough ~ 84 hours after dosing) criteria, also described in the Guidelines for Individual Dose Adjustment.

Dosing will continue up to 12 months in the absence of unacceptable toxicity or disease progression, or may be discontinued with Sponsor consent after completing at least 6 weeks of dosing.

B. Study Population

Up to 27 subjects 18 years or older with relapsed/refractory AML by World Health Organization (WHO) classification who have exhausted available therapy and who meet all inclusion/exclusion criteria will be enrolled at 3- 6 sites in the United States.

C. Sample Size Predictions

Formal sample size calculations are not applicable to this phase 1b/2a dose-adjustment and expansion study.

V. General Analytical Considerations

All analyses of safety and anti-leukemic activity for this open-label, early-phase study will be descriptive in nature and presented by dose group and overall, as appropriate, for dose-adjustment and expansion phases.

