Summary statistics will be presented for assigned dose level, cumulative assigned dose, cumulative actual exposure (mg), total duration of treatment (calculated as the number of weeks from date of first drug dose to date of last drug dose), dose intensity (calculated as cumulative actual exposure divided by treatment duration, mg/week), relative dose intensity (calculated as a percent of cumulative actual drug dose divided by cumulative assigned dose), and any reason for missed dose.

B. DHO Plasma Levels

In addition to safety/tolerability, intra-subject dosing for this study will be guided by DHO levels measured using a validated assay. A subject listing will include baseline and trough DHO levels (ng/ml), as well as the following additional characteristics noted at each scheduled visit:

- Previous assigned dose (mg/m²).
- DHO dose adjustment (dose not changed, escalated by 150 mg/m², held, Cohort 1 dose escalation not permitted).
- Assigned dose based on DHO (mg/m²).
- PI evaluation of whether subject has acceptable safety, safety dose adjustment, and assigned dose.
- Actual dose (mg).
- Agreement between PI assessment and actual dose (No/Yes, reason for disagreement).

The above dose-modification characteristics will also be summarized by treatment group and overall.

C. Dose Limiting Toxicities

AEs identified as protocol-defined DLTs will be listed and will include start and end dates, CTCAE grade, relationship to study drug, outcome, and action taken. Number and percentage of subjects reporting DLTs in each treatment group, and overall, will be summarized.

D. Adverse Events

AEs will be collected from time of informed consent through at least 14 days after the final dose of study medication. Any pre-existing condition that changes in severity after dosing or abnormal laboratory finding will be recorded as an AE. Events that occur prior to dosing will be recorded as medical history. A TEAE for this study will be defined as an AE occurring after the first dose of the study treatment through 30 days after the last dose of study treatment.

Verbatim terms on the eCRF will be coded using the MedDRA version 21.1 and displayed hierarchically by system organ class and preferred term. Multiple incidences of the same AE for a subject will be counted only once at the maximum CTCAE grade.

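### After Day 42, the Grade 4 neutropenia criterion stands without qualifiers between two qualified ones, so a subject with active leukemia can be classed either way

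*SAP*

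**What the plan says.** SAP Section III.A makes safety/tolerability a primary endpoint, "assessed at each study visit using the Common Terminology Criteria for Adverse Events (CTCAE) version 4.03", and sets criteria to be applied to each subject.

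- **Up to Day 42:** "Through Day 42, Grade 3 or higher, treatment-emergent, study drug-related, non-hematologic AE will be considered unacceptable toxicity", with a table of exceptions.
- **Later:** "After 42 days of treatment, criteria for unacceptable safety will be expanded to include hematologic AEs defined as", followed by three bullets:
  1. "Prolonged neutropenia with ANC < 500 from start of therapy in the absence of disease"
  2. "≥ Grade 4 neutropenia"
  3. "And/or ≥ Grade 4 thrombocytopenia with a hypocellular bone marrow and no greater than 5% marrow blasts lasting for ≥2 weeks"

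Section IV.B describes the population: "Up to 27 subjects 18 years or older with relapsed/refractory AML by World Health Organization (WHO) classification".

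Section VII.B lists the following for each scheduled visit and summarizes it by treatment group and overall: "PI evaluation of whether subject has acceptable safety, safety dose adjustment, and assigned dose".

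**The concern.** In relapsed/refractory AML, low neutrophil counts can come from the leukemia as well as from the drug. A safety criterion based on cytopenia therefore needs some way to separate the two. Bullet 1 does this by requiring that disease be absent. Bullet 3 does it with marrow cellularity, a blast limit and a minimum duration. Bullet 2, between them, has no such condition.

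Bullet 3 also opens with a conjunction, which is odd for a free-standing list item. It suggests that bullets 2 and 3 may have been one sentence, in which case the conditions at its end may have been meant for neutropenia as well. A reader of the SAP cannot tell.

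At stake is whether neutropenia that accompanies persisting leukemia counts against the drug in a primary endpoint, and whether investigators at different sites judge it by the same rule.

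**Working it through.** The point involves no sample size, power or event figure, and the plan gives no number to reproduce. The check treats the bullets as a logical rule and applies it to defined cases.

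**Inputs, all from SAP Section III.A**

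- B1: ANC below 500, prolonged from the start of therapy, disease absent.
- B2: neutropenia of Grade 4 or higher, with no further condition.
- B3: thrombocytopenia of Grade 4 or higher, hypocellular marrow, blasts not above 5%, lasting at least 2 weeks.

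**Two readings**

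- *As printed:* unacceptable if B1 or B2 or B3 is met.
- *Joined:* unacceptable if B1 is met, or if either Grade 4 cytopenia occurs together with the marrow, blast and 2-week conditions.

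**Cases, all after Day 42 with platelets not at Grade 4**

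| Case | As printed | Joined |
|---|---|---|
| (a) Grade 4 neutropenia, active leukemia with blasts above 5% | B1 no (disease present), B2 yes, B3 no: **unacceptable** | B1 no, joined criterion no (blasts too high): **not unacceptable** |
| (b) Grade 4 neutropenia that began after Day 42 and lasted under 2 weeks, hypocellular marrow, blasts not above 5% | B1 no (not from start of therapy), B2 yes, B3 no: **unacceptable** | B1 no, joined criterion no (too short): **not unacceptable** |
| (c) Grade 4 neutropenia of at least 2 weeks, hypocellular marrow, blasts not above 5% | B2 yes: **unacceptable** | joined criterion yes: **unacceptable** |

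The readings agree on (c) and give opposite answers on (a) and (b). Case (a) is the one that matters most in this population.

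**Joining the lines is not enough.** In the joined sentence the closing conditions could still be read as belonging to thrombocytopenia alone. Neutropenia would then be unqualified again, with the same result as the printed version. The scope of the conditions has to be stated.

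**Relation of B2 to B1.** The SAP does not print the ANC limit for Grade 4. If it is taken as ANC below 500 (an assumption), any B1 neutropenia still present after Day 42 already meets B2, and the absence-of-disease condition in B1 then changes nothing. Cases (a) to (c) do not depend on this assumption.

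**Does another section resolve it?**

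- Section VII.B reports the investigator's view of acceptable safety and does not restate the rule.
- Section VII.C lists protocol-defined DLTs and does not tie them to these bullets.
- Section VII.D tabulates adverse events by term and grade, without marrow status.
- The graded shift tables in Section VII.F cover leukocytes, hemoglobin and platelets, not neutrophils.

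None of these says which conditions govern neutropenia, and none would show how many subjects the two readings separate.

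**The case against.** **This is a line break, not two rules.** The opening conjunction makes a split sentence likely, and the joined version fits the disease condition in bullet 1. The split may also come from reading the PDF, although the full stop after neutropenia and the capital letter that follows speak against a pure reading error. This stands as an explanation of how the text arose. It does not remove the problem, since the printed text can be followed literally and the joined text still has two meanings.

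**The drug-relationship limit carries over.** The later criteria expand on a criterion restricted to treatment-emergent, study drug-related events. Carrying that restriction forward is plausible and would exclude neutropenia attributed to leukemia. But the SAP does not repeat it, and the hematologic events have their own definition list. Even with carry-over, the scope of the marrow and duration conditions stays open.

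**Baseline neutropenia is not clearly an adverse event.** Section VII.D treats events before dosing as medical history and records a pre-existing condition as an adverse event if its severity changes. Unchanged leukemic neutropenia might therefore never reach the criteria. This narrows the effect in part, because the same section also names abnormal laboratory findings, and neutropenia that worsens under persisting leukemia still qualifies.

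**No analysis depends on it.** The SAP describes no derived variable built from these bullets, and all analyses are descriptive (Section V). This stands as a real limit on impact. The investigators' evaluation is nevertheless summarized by treatment group, and Section IV.B plans 3 to 6 sites, so those judgments need one definition.

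**The protocol may have the intact sentence.** It may; only the SAP was examined. But the SAP prints its own version and gives no protocol section for it, whereas it does cite protocol sections for response definitions and dose adjustment.

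**Conclusion.** The point holds as a defect in the definition of a primary endpoint. Followed literally, the text classes Grade 4 neutropenia with active leukemia as unacceptable safety. Under the joined reading, with shared conditions, the same subject is not so classed. The SAP does not resolve this.

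Its size is a reversed classification for each subject in case (a) or (b). The SAP gives no basis for estimating how many there will be, so no rate is stated.

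Three stronger conclusions that a reader might infer are not supported:

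- *That the bullets contradict each other.* They are alternatives, and no two figures disagree. The fault is unclear scope of the qualifiers.
- *That bullet 2 certainly cancels the disease condition in bullet 1.* This needs the Grade 4 limit, which the SAP does not print.
- *That reported safety results will be inflated by a programmed count.* No such derivation is described, and investigator attribution or adverse event status may exclude some cases.

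The correction is worth making before database lock because the wording concerns a primary endpoint. It does not put the descriptive safety tables as a whole in doubt.

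**What to change.** 1. Reconcile the three bullets with each other and with the protocol text. Which clinical rule should apply is for the sponsor and the protocol.
2. Write the result as separate, complete statements for neutropenia and for thrombocytopenia. For each, say yes or no to four qualifiers: absence of disease, marrow findings (cellularity and blasts), minimum duration, and relationship to study drug.
3. Refer to that reconciled definition wherever acceptable safety is evaluated and summarized, in particular in Section VII.B.
4. If the classification is tabulated, give the number of subjects meeting each criterion separately, so that a reader can see which one drives the total.

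The cost is a few lines of SAP wording, plus one small table if step 4 applies. If the protocol has the same split, its wording needs the same clarification.

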Statistical code and outputs for analyses will be generated using SAS/STAT and SAS/GRAFH software, version 9.3 or higher, of the SAS system for Windows. Copyright © [2011] SAS Institute Inc. SAS and all other SAS Institute Inc. product or service names are registered trademarks or trademarks of SAS Institute Inc., Cary, NC, USA.

A. Data Sources

The study center staff will record completion and results of required study procedures in an electronic case report form (eCRF). The following external data obtained from third-party vendors for this study will be combined with eCRF data for analysis:

Vendor Name	Contact Information	Data Type	Schedule	Reconciliation Items
Pyxant	TBD	DHO plasma levels and brequinar PK results	2 transfers during study	Header data (subject ID, initials, visit, lab date, lab time)

B. Multiple Study Centers

Data analyses will be pooled and not controlled for center effect.

C. Definition of Baseline

Baseline will be defined as the last measurement collected before the first dose of study drug. As such, height and body surface area assessed at Screening, and pre-dose assessments made on Cycle 1 Week 1 Day 1 for weight, vital signs, hematology/chemistry, and 12-lead ECG will serve as valid baseline measures. A missing value at Cycle 1 Week 1 Day 1 will default to the Screening measurement.

For this study, since there is no day 0, the day immediately prior to study day 1 will be Day -1 [calculated as Event Date – Date of First Treatment]. For events on or after first dose of study drug, study day will be calculated as [Event Date – Date of First Treatment + 1]. Thus, first day of study drug dose will be Day 1.

D. Missing Data

Unless stated otherwise in sections below, missing data will not be replaced with imputed values.

E. Analysis Populations

Four analysis population sets will be defined for use with various analyses, namely:

- The Enrolled Analysis Set will include all subjects who sign informed consent, meet the inclusion/exclusion criteria and are enrolled in the study. Demographics and disposition summaries will be reported for this set of subjects.
- The Safety Analysis Set will include all subjects who are enrolled in the study and receive at least one dose of brequinar. Subjects in this set will be used for all safety/tolerability summary tables.

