- The Efficacy Analysis Set will be a subset of the Safety population with measurable AML disease at baseline and at least one post-baseline disease response assessment. Subjects in this set will be used for all efficacy summary tables.
- Pharmacokinetic Analysis Set will be a subset of the Safety population with at least 1 quantifiable plasma concentration collected post-dose without important protocol deviations/violations or events thought to significantly affect the PK. Summary tables for PK concentrations and parameters will be based on this set of subjects.

F. Data Display Characteristics

Data displays produced for this study will include three types—data listings, summary tables, and figures.

Unless stated otherwise, data listings will be produced for all recorded data. Data listings will simply list the data recorded on the CRF or derived for each subject. They will be ordered by treatment, subject number, and date and time of assessment, where applicable. When expedient, additional levels of ordering hierarchy may reflect subsets of assessments within subject. Additional listings may be produced for outcome measures that involve extensive procedure to derive analyzed outcomes.

Summary tables will display summary statistics calculated for each of the treatment groups, and overall. When the evolution of statistics over time is of interest, a group of rows that represent a cohort would generally be ordered chronologically.

The summary statistics displayed will be a function of the type of data associated with the summarized assessment. Continuous data will be summarized with the number of nonmissing values, mean, standard deviation (SD), minimum, median, and maximum. Categorical data will be summarized with the number of nonmissing values. Corresponding percentages will be calculated using the relevant analysis population set as the denominator, unless stated otherwise. Some continuous variables may also be grouped into categorical levels and evaluated in frequency tables.

PK concentrations and parameters will be summarized using n (for available data), mean, SD, coefficient of variation percent (CV%), median, minimum, and maximum values. Geometric means and geometric CV% will also be calculated for PK parameters.

All PK concentrations will be reported and analyzed with the same precision as the source data provided by the bio-analytical laboratory regardless of how many significant figures or decimals the data carry.

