Extra measurements (such as unscheduled or repeat assessments) will be included in subject listings but not in summary tables.

Figures will be produced as specified in sections to follow.

VI. Subject Accountability

A. Analysis Populations

A summary table will present counts and percent of subjects in the study analysis populations of Enrolled, Safety, Efficacy, and PK Analysis sets by treatment group.

B. Disposition

All subjects who discontinue treatment or withdraw early from the study will be included in a listing. Disposition summaries will present number of subjects enrolled, number treated, and among those treated number who completed and discontinued treatment. Primary reason for discontinuation of treatment, including any of the following, will be summarized:

- Adverse event
- Physician/Sponsor decision
- Pregnancy
- Protocol defined disease progression
- Study terminated by sponsor
- Subject non-compliance/Protocol violation(s)
- Withdrawal of consent.

Counts and percentages of subjects who withdraw early from the study for any of the above reasons will also be calculated using all members of the relevant population in the relevant treatment group for the denominator.

C. Subject Characteristics

The following subject characteristics collected for the Enrolled Analysis Set will be presented in data listings and summarized by treatment regimen and overall:

Demography:

- Age: Age will be calculated as the number of years elapsed between birth date and the date of the screening visit, adjusted for whether the birthday has passed as of the day of the screening visit.
- Sex at birth
- Ethnicity
- Race

Medical History:

- Medical history: As noted on the Medical History eCRF, any significant medical conditions present prior to signing consent will be presented in a listing and summary table. Verbatim terms will be coded using the MedDRA version 21.1 and ordered by system organ class (SOC) and preferred term (PT). At each level of summation (SOC, PT), subjects reporting more than one medical condition will be counted only once.
- AML disease information: Disease characteristics of initial diagnosis of AML recorded on the eCRF, along with time since initial diagnosis (calculated as date of informed consent – date of initial diagnosis of AML/365.25), will be listed and summarized.

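### The Enrolled Analysis Set carries an eligibility condition that the Safety set lacks, so a dosed subject found ineligible would be in the safety tables but not in the baseline and disposition tables

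*SAP*

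**What the plan says.** Section V.E (Analysis Populations) gives the Enrolled set three joint conditions: "The Enrolled Analysis Set will include all subjects who sign informed consent, meet the inclusion/exclusion criteria and are enrolled in the study". It then assigns the set its use: "Demographics and disposition summaries will be reported for this set of subjects".

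The next definition in the same section has two conditions and does not mention eligibility: "The Safety Analysis Set will include all subjects who are enrolled in the study and receive at least one dose of brequinar".

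Section VI.C (Subject Characteristics) ties both tables and listings to the Enrolled set: "The following subject characteristics collected for the Enrolled Analysis Set will be presented in data listings and summarized by treatment regimen and overall". Demography, medical history, AML disease information, supplemental tests and prior cancer treatment all fall under that sentence.

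Section VI.B (Disposition) says: "Disposition summaries will present number of subjects enrolled, number treated, and among those treated number who completed and discontinued treatment". Section VI.D provides a listing of protocol deviations. It does not say what an eligibility deviation does to membership of any analysis set.

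**The concern.** Because being enrolled is listed as its own condition, meeting the criteria works as a further filter. A subject can pass the first and third conditions and fail the second. If that subject has been dosed, the Safety definition still takes the subject in.

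The study's primary objective includes safety and tolerability, and the cohorts are very small. Readers will interpret the toxicity rates against the age, AML history, prior therapy and reasons for discontinuation of the same subjects. If the baseline and disposition tables rest on a narrower group, that link is broken for the omitted subject. The denominators of the two sets of tables also differ, and the SAP does not explain why.

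**Working it through.** There is no calculation in the plan to reproduce here. The check compares the definitions and then sizes the effect from the cohort numbers.

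**Step 1: the definitions side by side (section V.E).**

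| Condition | Enrolled set | Safety set |
|---|---|---|
| Consent signed | required | not stated |
| Meets eligibility criteria | required | not stated |
| Enrolled in the study | required | required |
| At least one dose | not required | required |

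**Step 2: the test case.** Take a subject who consents, is enrolled and dosed, and is then found to have breached a criterion.
- Enrolled set: fails the second condition, so out.
- Safety set: meets both of its conditions, so in.
- Efficacy and PK sets: these are subsets of Safety, so the subject is in if their own further conditions are met.

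The Safety set is therefore not contained in the Enrolled set.

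**Step 3: which outputs are affected.**
- Lost: the disposition summaries (V.E, VI.B) and the subject-characteristics tables and listings (VI.C).
- Kept: all safety analyses (section VII uses the Safety set), the listing of subjects who discontinue or withdraw (VI.B, not restricted to the Enrolled set), the deviation listing (VI.D) and the AE listing (VII.D).

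**Step 4: size.** Section IV.A gives 5 subjects in Cohort 1 (6 were planned), about 6 in Cohort 2 and about 15 in expansion. The planned total is 6 + 6 + 15 = 27, which matches the stated maximum. With Cohort 1 closed at 5 it is 5 + 6 + 15 = 26.

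Share of the group that one omitted subject represents, 1/n:
- Cohort 1: 1/5 = 20.0%
- Cohort 2: 1/6 = 16.7%
- Expansion: 1/15 = 6.7%
- Overall: 1/26 = 3.8%

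Example: with six treated in Cohort 2 and one breach, the section VI.A table of analysis populations would show Enrolled 5 and Safety 6. If the disposition table is restricted wholly to the Enrolled set, its number treated also falls to 5. The mismatch then shows in VI.A and against the safety tables, not within the disposition table.

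**Step 5: how likely a breach is.** The SAP gives no rate. As an assumption only, with independent subjects and breach probability p each, the chance of at least one breach among 26 is 1 − (1 − p)^26:
- p = 2%: 41%
- p = 5%: 74%
- p = 10%: 94%

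**The case against.** The strongest reply is that the Enrolled definition simply names the steps of entry in order. Section IV.B supports this, since it says that subjects "who meet all inclusion/exclusion criteria will be enrolled at 3- 6 sites in the United States". On that view, a subject judged eligible at screening and entered has satisfied the definition. Nothing in section V.E calls for a later re-check or for removing anyone. The protocol, which is not shown, may also define enrolment and the handling of eligibility breaches. This reading is possible, but it makes the eligibility clause redundant, and the SAP does not say that eligibility is fixed at the screening judgement. A programmer who applies the three conditions to final data would exclude the subject. Deleting the clause is harmless on one reading and corrective on the other.

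It is also fair to say that the subject does not vanish from the report. The listings in step 3 remain, section VI.A would display a mismatch in counts, and discontinuation for a protocol violation is itself a summarised category in section VI.B. All of this stands and limits the scope to the outputs named above.

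A reader might go further and infer that the subject also drops out of the Safety set, and with it out of the efficacy and PK results, by taking enrolled to mean membership of the Enrolled Analysis Set. The SAP does not support that. The Safety definition refers to enrolment in the study, not to the Enrolled set. Where the SAP wants nesting it says so: "The Efficacy Analysis Set will be a subset of the Safety population with measurable AML disease at baseline" and "Pharmacokinetic Analysis Set will be a subset of the Safety population with at least 1 quantifiable plasma concentration". And the Enrolled definition treats being enrolled as distinct from being eligible, so the same phrase in the Safety definition most naturally means the plain act of entry.

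**Conclusion.** The point holds for the baseline and disposition outputs only. As written, the Enrolled set can exclude a subject whom the Safety set includes, so the two sets do not nest and the section VI.C and disposition tables may omit a treated subject. The size is one subject per breach: 20% of Cohort 1, about 16.7% of Cohort 2, about 6.7% of expansion and 3.8% of 26 overall.

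The conclusion rests on two conditions: that at least one eligibility breach occurs, and that the definition is applied literally to what is known at analysis. The SAP reports no breach, the cohort sizes other than Cohort 1 are approximate, and the breach rates in the check are assumptions. The analyses of safety and anti-leukemic activity are descriptive, so no test or decision threshold moves. Nothing in the document shows that an omitted subject would be frailer than the rest or that any toxicity would go unreported. Importance is low to moderate.

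**What to change.** In section V.E, remove the eligibility condition from the Enrolled Analysis Set. The set then holds everyone who gave consent and was enrolled, regardless of any eligibility deviation identified later. Add one sentence stating that every subject who received brequinar belongs to both the Enrolled and the Safety sets. In section VI.D, mark eligibility deviations as such in the listing, so that a reader can see which subjects are concerned.

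The cost is a few words of SAP text, with no new data and no extra subjects. It should be done before database lock, so that set membership is not decided with the results in view.
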